10. SAMPLE SIZE

A total of six NHS trusts in England (n=4) and Wales (n=2) will participate in the study.

Within each trust, a questionnaire survey of acute inpatient staff (n per Trust/Health Board=50; total=300), service users (n=50; total=300) and carers (n=25; total=150) that currently or have recently used acute adult inpatient mental health services will be conducted.

Within each trust/health board, one ward will participate in micro-level data collection. Semi-structured interviews with staff (n per ward=6; total=36), service users (n per ward =6; total=36; to include joint review of care plan) and carers (n per ward=4; total=24) will be conducted. Structured case reviews of care plans will be conducted for service users on each participating ward (n per ward = 10; total = 60). Non-participant observation of care planning processes on inpatient units (n per ward=3; total=18)

Justification of the sample size, and the effect size

For the questionnaire survey, an a priori sample size calculation was conducted using the software package G*Power. The sample size was based on completing a multivariate analysis (MANCOVA) for comparing the interaction of within (Covariates) and between factors (sites). Assumptions are based on six groups (sites), four outcome measures (questionnaires) and 10 potential predictors (i.e. gender, age, ethnicity, and time on CPA etc.). We calculated sample size using α level of 0.05, power of 0.80 (Cohen, 1992) and a small effect size (Pillai's Trace V = 0.10). Given the many potential influences on our outcome measures we anticipate that the magnitude of the observed relationship will be

small. A small effect size was therefore chosen in order to represent the subtleties in relationships of the data. This calculation suggests that a sample size of 276 is required in order to reach power.

In our study we aim to obtain complete questionnaire survey responses from 300 service users (approx. n =50 per site) 300 inpatient staff (approx. n =50 per site) and 150 informal carers (approx. n =25 per site). By sampling 300 survey responses we are sampling in excess of the sample size suggested for the service users and inpatient staff. In contrast, we anticipate that we will not achieve this sample size for informal carers. This is because not every service user will have a carer therefore analysis for the informal carers will be underpowered (estimated power will be 0.44). The data for the informal carers will be exploratory in preparation for a future larger scale study. We anticipate that with non-response and incompletion of the questionnaires we will need to oversample in order to meet the sample sizes.

Calculations for the sample size for qualitative interviews were based on previous research with similar populations by the co-investigators and others; understanding of the practicalities and time commitments of recruiting and interviewing participants and analysing in-depth qualitative data; and the numbers required to feel confident that the findings would be transferable to other similar settings.

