Questionnaire returns for each site will be entered, checked and cleaned using SPSSv21. The distribution of questionnaire data (VOICE, RSA, STAR and ES) will be assessed for normality by exploring the data graphically using plots and numerically using statistical methods (Shapiro-Wilk and Kolmogorov-Smirnof tests). Descriptive statistics will be calculated and presented in order to provide an overview of clinically significant findings prior to statistical interpretation. To ascertain any differences between the six sites on the four outcome measures for service users, (VOICE, RSA, STAR and ES) a one-way Multivariate Analysis of Covariance (one-way MANCOVA) will be conducted. Covariates will reveal if there are any external influencing factors in care or if these are result of within-case (site) effects. Potential covariates will be patient demographics (i.e. age, gender, ethnicity, diagnosis, and civil/family/accommodation/employment status), diagnosis (type of severe mental illness), and service use (informal/formal, frequencies of admissions, length of stay/service use) and clinical variables (number of staff on ward number of patients). If statistically significant differences are found subsequent One-way Analysis of Covariance (One-way ANCOVA) will be employed post hoc to ascertain which measures differ between which locations. Correlations will be carried out to identify if there is a relationship between the outcome measures. The type of correlation that will be performed will be informed by hypotheses

derived from the descriptive data and the qualitative data. Selective correlations will be conducted using Multiple Linear Regression. Similarly a one-way MANCOVA will be conducted to analyse staff questionnaires (RSA and STAR) with appropriate post hoc analyses. A one-way ANCOVA will be used to analyse the carer questionnaire (RSA) and if significant differences are found Tukey's post hoc test will be conducted.

Qualitative analysis

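### The required 276 is sized for a 10-df, four-outcome test, which is neither the interaction section 10 names nor the site comparisons section 11 plans

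*Protocol*

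**What the plan says.** Section 10 (Justification of the sample size, and the effect size) describes an a priori G*Power calculation and names its target: "The sample size was based on completing a multivariate analysis (MANCOVA) for comparing the interaction of within (Covariates) and between factors (sites"). The inputs follow. "Assumptions are based on six groups (sites), four outcome measures (questionnaires") and 10 potential predictors are assumed, with "a small effect size (Pillai's Trace V = 0.10"), alpha 0.05 and power 0.80. The result is: "This calculation suggests that a sample size of 276 is required in order to reach power".

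The section then says that 300 service users and 300 staff exceed this requirement. It also says that 150 carers will be underpowered, with estimated power 0.44, so the carer data are treated as exploratory.

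Section 11 (Quantitative analysis) plans a one-way MANCOVA for service users: "To ascertain any differences between the six sites on the four outcome measures" (VOICE, RSA, STAR and ES), with covariates. Staff get a one-way MANCOVA on two measures (RSA and STAR). Carers get a one-way ANCOVA on one measure (RSA). No site-by-covariate interaction is planned for any group.

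**The concern.** A sample size supports a claim only about the hypothesis it was computed for. Section 10 names an interaction, its inputs imply a joint test of ten predictors, and section 11 tests site. These three have different degrees of freedom, so a single N cannot give 0.80 power for all of them.

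Two consequences follow. A reader of section 10 will believe that site-by-covariate interactions have at least 80% power at 300, and may then read a null interaction as informative. The power of the tests that will actually be run is not stated for any of the three groups, and the one group-specific power given (carers, 0.44) appears to belong to a different model.

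**Working it through.** **Method.** Noncentral F for Pillai's trace, as in G*Power's MANOVA module for special effects and interactions. Let p = outcomes, q = df of the tested effect, g = groups = 6, and s = min(p, q). Then:

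- f² = V/(s − V)
- df1 = p·q
- df2 = s(N − g − p + s)
- noncentrality λ = N·s·f² (O'Brien-Shieh); the alternative is λ = df2·f² (Muller-Peterson)
- power = P[F(df1, df2, λ) exceeds the upper 5% point of the central F]

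**Inputs.** V = 0.10, alpha 0.05, power 0.80, six groups, four outcomes and 10 predictors are from section 10. The two staff outcomes and one carer outcome are from section 11.

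**The plan's own 276 (p = 4, q = 10).**

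- f² = 0.10/3.90 = 0.02564
- df1 = 40
- df2 = 4 × (276 − 6 − 4 + 4) = 1080
- λ = 276 × 4 × 0.02564 = 28.31
- power = 0.801

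N = 275 gives 0.799, so 276 is the exact solution. Muller-Peterson gives 282. Nearby choices do not match under O'Brien-Shieh: q = 9 gives 264 and q = 15 gives 328. Reading 0.10 as f² instead of V gives 76.

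**Cross-check on the carer figure.** The same set-up at N = 150 has df2 = 576, λ = 15.38 and power 0.437, which is the stated 0.44. Two figures in section 10 therefore identify the calculation as p = 4, q = 10.

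**The planned and named tests, V held at 0.10 (O'Brien-Shieh).**

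| Test | p | q | f² | N for 0.80 | Power at planned N |
|---|---|---|---|---|---|
| Service users, site | 4 | 5 | 0.0256 | 209 | 0.947 at 300 |
| Service users, site × ten 1-df covariates | 4 | 50 | 0.0256 | 566 | 0.385 at 300 |
| Staff, site | 2 | 5 | 0.10/1.90 = 0.0526 | 159 | 0.987 at 300 |
| Carers, site | 1 | 5 | 0.10/0.90 = 0.1111 | 122 | 0.891 at 150 |

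The site effect has 6 − 1 = 5 df, and the interaction has 5 × 10 = 50. The service-user site test at 276 has power 0.923. With Muller-Peterson the four Ns are 215, 572, 165 and 127, and the carer power is 0.876. Removing ten covariate df from error as well leaves the service-user N at 209 (O'Brien-Shieh) or raises it to 225 (Muller-Peterson).

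**How far the staff and carer figures depend on holding V.** V is bounded by s, so V = 0.10 implies a larger f² when there are fewer outcomes (see the table). If f² = 0.02564 is held instead:

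- Carers at 150: λ = 150 × 1 × 0.02564 = 3.85 on 5 and 144 df, power about 0.27.
- Staff at 300: λ = 300 × 2 × 0.02564 = 15.38 on 10 and 588 df, power about 0.76.

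Neither convention gives 0.44 for carers.

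**The case against.** The arithmetic of 276 is right for its inputs, and the mismatch is conservative for the service-user site test: 276 is more than the 209 needed. The study calls itself exploratory, and much of its weight rests on qualitative work. Section 11 also says that covariates are of interest, so a calculation built on predictors is not wholly foreign to the plan. All of this stands. It limits the harm to a mis-described justification, but it does not make the description correct. Section 10 names an interaction that section 11 does not test, and 276 would be far too small for it.

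One could rescue the wording by supposing a 10-df interaction, such as site (5 df) with a single 2-df covariate block. The text speaks of ten separate predictors, so this reading has no support.

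Three stronger readings are tempting, but the protocol does not bear them out:

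- That the survey is underpowered for its main comparison. On the stated inputs it is not.
- That the covariate lists in sections 10 and 11 contradict each other. Both are offered as potential candidates, so a difference between them is not an inconsistency and does not alter 276.
- That the word used for the covariates in section 10 claims a repeated-measures factor. It is poorly chosen, but the text does not say that.

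**Conclusion.** The point holds as a mismatch between the sample-size justification and the planned analyses. The stated 276 and the carer power of 0.44 both come from a 10-df, four-outcome test that section 11 does not specify. With V = 0.10, the planned service-user site test needs about 209 to 215 and has power of about 0.95 at 300. The interaction named in section 10 would need about 566 and has power of about 0.39 at 300. Staff need about 159 for their two-outcome site test. The carer ANCOVA has power of about 0.89 at 150.

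These figures ignore clustering and count each covariate in the interaction as 1 df; multi-category covariates would raise its df. They also hold V at 0.10, the only effect size given, although it means something different for each test. For that reason a reader should not infer that the carer analysis is now shown to be well powered. The 0.89 corresponds to an f² of 0.111, and power falls to about 0.27 if the service-user f² is held instead. What is established is that 0.44 is not the power of the planned carer test.

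**What to change.** In section 10:

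- Delete the wording about an interaction of covariates and sites.
- State the calculation for the site effect (5 df) separately for service users (four outcomes, power at 300), staff (two outcomes, power at 300) and carers (one outcome, power at 150), giving the effect size assumed for each and the noncentrality option used.
- Replace the carer power of 0.44 with the figure for the planned one-outcome ANCOVA.
- State that covariate effects and site-by-covariate interactions are not powered.

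The cost is a reworded paragraph and three short calculations. Recruitment targets of 300, 300 and 150 and the analyses in section 11 do not change.

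### The carer power of 0.44 and the 276 behind the staff statement come from a four-outcome calculation; carers have one outcome and staff two, so 0.44 is wrong for the planned analysis and the staff statement is unsupported

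*Protocol*

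**What the plan says.** Protocol section 10 (justification of the sample size) describes a single G*Power calculation. Its target is a "multivariate analysis (MANCOVA) for comparing the interaction of within (Covariates) and between factors (sites"). The inputs are: "Assumptions are based on six groups (sites), four outcome measures (questionnaires) and 10 potential predictors", with "α level of 0.05, power of 0.80" and "a small effect size (Pillai's Trace V = 0.10"). The result is a required sample of 276.

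That result is then carried to the other groups. For service users and staff: "By sampling 300 survey responses we are sampling in excess of the sample size suggested for the service users and inpatient staff". For carers, where 150 complete responses are expected: "therefore analysis for the informal carers will be underpowered (estimated power will be 0.44"). The carer data are declared exploratory.

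Section 11 (quantitative analysis) and the synopsis plan a MANCOVA of VOICE, RSA, STAR and ES for service users only. For staff: "Similarly a one-way MANCOVA will be conducted to analyse staff questionnaires (RSA and STAR"). For carers: "A one-way ANCOVA will be used to analyse the carer questionnaire (RSA"). The instrument descriptions in section 8 agree: carers are given the RSA alone, and staff the RSA and STAR.

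**The concern.** The power of a multivariate test depends on the number of outcomes, both through its degrees of freedom and through the conversion of V into an effect per dimension. A figure worked out for four outcomes is not the figure for one or two. If 0.44 and 276 both come from the four-outcome set-up, the protocol prints a carer power for an analysis that cannot be run on carers, and it reassures the reader about staff from a requirement that is not theirs.

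A reader will use these numbers. Section 11 still plans a significance test of the carer data with Tukey follow-up, and a null result would be read against 0.44. The carer data are also meant to prepare a larger study. For staff, the comparison of 300 with 276 is the only support offered for the sample.

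**Working it through.** **Inputs (protocol section 10).** g = 6 sites; p = 4 outcomes; q = 10 predictors; V = 0.10; α = 0.05; power 0.80; planned complete responses 300 (service users), 300 (staff) and 150 (carers). From section 11: p = 2 for staff, p = 1 for carers.

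**Formulas (Pillai F approximation as used in G*Power).** s = min(p, q); f² = V/(s − V); df1 = p·q; df2 = s(N − g − p + s); λ = N·s·f². Power is the upper tail of the noncentral F beyond the 5% critical value.

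**Step 1: reproduce the printed figures (p = 4, q = 10).**
- s = 4; f² = 0.10/3.90 = 0.0256; df1 = 40.
- N = 276: df2 = 4 × (276 − 6 − 4 + 4) = 1080; λ = 276 × 4 × 0.0256 = 28.3; power 0.801. At N = 275 it is 0.799, so 276 is the exact requirement.
- N = 150: df2 = 4 × (150 − 6 − 4 + 4) = 576; λ = 15.4; power 0.437, which rounds to 0.44.

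One set of inputs gives both figures. The alternatives tried do not: λ = f²·df2 gives 282 and 0.417; q = 5 gives 209 and 0.61; reading 0.10 as f² gives N = 76.

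**Step 2: what carries over to fewer outcomes.** V = 0.10 implies a different effect per dimension as s changes:
- four outcomes: 0.10/3.90 = 0.0256
- two outcomes: 0.10/1.90 = 0.0526
- one outcome: 0.10/0.90 = 0.1111

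The protocol does not say whether V or f² is meant to be common to the groups, so both are shown. It also does not say which effect would be tested for staff and carers, so q = 10 (its predictor count) and q = 5 (the six-site effect) are both shown.

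**Step 3: carers, p = 1, N = 150.** df2 = 150 − 6 − 1 + 1 = 144. λ = 150 × 0.1111 = 16.7 with V held, or 150 × 0.0256 = 3.85 with f² held.

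| Held constant | q | Power at 150 | N for 0.80 |
|---|---|---|---|
| V = 0.10 | 10 | 0.78 | 156 |
| V = 0.10 | 5 | 0.89 | 122 |
| f² = 0.0256 | 10 | 0.20 | 643 |
| f² = 0.0256 | 5 | 0.27 | 506 |

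A carer power of 0.44 would need V of about 0.054 (q = 10) or 0.041 (q = 5). The protocol states neither.

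**Step 4: staff, p = 2, N = 300.** df2 = 2 × (300 − 6 − 2 + 2) = 588. λ = 300 × 2 × 0.0526 = 31.6 with V held, or 300 × 2 × 0.0256 = 15.4 with f² held.

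| Held constant | q | N for 0.80 | Power at 300 | 300 enough? |
|---|---|---|---|---|
| V = 0.10 | 10 | 207 | 0.95 | yes |
| V = 0.10 | 5 | 159 | 0.99 | yes |
| f² = 0.0256 | 10 | 417 | 0.61 | no |
| f² = 0.0256 | 5 | 322 | 0.765 | no |

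Taking 10 covariates out of the error degrees of freedom changes these powers by about 0.002 or less and the required N by at most 1.

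**The case against.** The strongest reply concerns staff. A reader might infer that the staff sentence is false, because 276 is not the staff requirement and 300 falls short of 322 to 417. The documents do not support that. The only effect size the protocol states is V = 0.10, and at that value the two-outcome requirement is 159 to 207, which 300 clears comfortably. The value f² = 0.0256 is printed nowhere; it is derived from V with four outcomes. The sentence lacks a calculation, but it has not been shown to be untrue. This objection stands.

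A reader might also infer that the carer analysis is in fact adequately powered, or that it is far weaker than stated. Neither follows. The two readings of the effect size point in opposite directions, and power stays below 0.80 in three of the four scenarios. The word underpowered may therefore survive even though the number does not.

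The carer data are declared exploratory, the protocol attributes the shortfall to too few service users having carers, and no decision rule rests on 0.44. That limits the consequence but does not make the number right. Nor is this a detail left to a separate analysis plan: the figure is printed in section 10 and conflicts with the analysis in section 11.

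Finally, nothing obliges the protocol to use one common effect size per outcome for all three groups. Different assumptions are defensible if each is stated.

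**Conclusion.** The point holds for carers as an error and for staff as a missing justification. The 0.44 is the power of a four-outcome, 10-predictor MANCOVA at N = 150. The planned one-outcome ANCOVA has power of 0.78 or 0.89 at V = 0.10, or 0.20 or 0.27 at f² = 0.0256, and no reading tried returns 0.44. The direction of the error cannot be settled from the protocol. The staff statement holds at V = 0.10 and fails at f² = 0.0256, so it is unsupported.

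The service-user figure of 276 reproduces from its stated inputs and is not challenged here. The 10-predictor set-up matches the service-user analysis in its number of outcomes; whether it is the right effect to power on is a separate question.

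The results assume the Pillai F approximation, complete responses at the planned numbers, and independent respondents; clustering within wards is ignored. This should be fixed because a stated power is wrong, but it is not critical for a group declared exploratory.

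**What to change.** In section 10:

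- say that 276 applies only to the four-outcome service-user analysis;
- delete 0.44 and print the power of the one-outcome carer ANCOVA at N = 150;
- add a two-outcome calculation for staff at N = 300;
- for each group, state the effect size assumed and the effect tested (the 5-df site comparison or the 10-predictor effect);
- reword the sentence calling carers underpowered and the sentence calling 300 staff more than sufficient, so that each matches its result.

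The cost is a recalculation and a few sentences. Recruitment targets need not change. The price is that a stated power may become less favourable: if f² = 0.0256 is the intended effect, the staff power at 300 would have to be reported as 0.61 or 0.765 and the carer power as 0.20 or 0.27.

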11. DATA ANALYSIS

Analytical framework

This study involves a range of methods including policy review, narrative synthesis, cross-sectional survey, and semi-structured interview methods. Accordingly several distinct approaches to the analysis of findings will be used.

We will frame our data analysis by drawing on social scientific ideas and on the findings of our Phase 1 evidence and policy review, an approach we have used in previous funded studies e.g. Hannigan (2013). Our concern to explore commonplace practices in inpatient mental health settings is congruent with interactionist interests in social processes and human action (Atkinson & Housley 2003). This perspective also recognises the importance of social structures, so that in any given setting person-to-person negotiations are shaped by features of organisational context (Strauss 1978). The immediate context for frontline practitioners/service users in this study is the inpatient unit, each of which we view as a complex, open system. Each participating ward also sits within a larger, meso-level, NHS Trust/Health Board site, which in turn is located within a national-level system of mental health services. This idea of 'nested systems' is a feature of complexity thinking (Byrne 1998), and informs our plan to generate, analyse and connect data at different (but interlocking) macro/meso/micro 'levels' of organisation.

Our Phase 1 policy and literature review will allow us to compare and contrast the largest-scale (or 'macro-level') systems for mental health care across the two countries, and

consider the degree to which ideas of recovery and personalisation are represented in prevailing frameworks. We will analyse what managers and professionals say, and write, about care planning and coordination across participating sites to make the connections between the 'macro' and the 'meso', and in the first instance we will present a detailed account of our six different local organisational contexts in within-case fashion (Ayres et al 2003). The most important phase of our data analysis will be our exploration of what frontline practitioners, service users and carers say, and write, about how actual, individual (or 'micro')-level care is planned and coordinated. We will establish the day-to-day realities of how care is planned and experienced in inpatient settings and the degree to which processes and actions reflect orientations to recovery and personalisation.

Data management

The study will involve the collection and storage of a large volume of data. The research team have a reliable, structured and transparent system for collating, recording, storing, checking, anonymising and analysing a large volume of quantitative and qualitative data collected by site and data type, informed by experience of managing data in the COCAPP project. Members of the research team at City University will continue to manage this process with input and support from colleagues in Wales. We have an established encrypted system for transcription and transfer of qualitative data and all quantitative data will be collated and inputted on SPSS at City University London. We are using a recognised method of handling multiple sources from different sites with the aid of QSR NVivo10 software and Framework method. The team have received bespoke training in the use of Framework for this study provided by the National Centre for Social Research (NatCen). We will first conduct a series of within-case analyses, treating each of our six NHS sites as a 'case' for this purpose.

Quantitative analysis

Questionnaire returns for each site will be entered, checked and cleaned using SPSSv21. The distribution of questionnaire data (VOICE, RSA, STAR and ES) will be assessed for normality by exploring the data graphically using plots and numerically using statistical methods (Shapiro-Wilk and Kolmogorov-Smirnof tests). Descriptive statistics will be calculated and presented in order to provide an overview of clinically significant findings prior to statistical interpretation. To ascertain any differences between the six sites on the four outcome measures for service users, (VOICE, RSA, STAR and ES) a one-way Multivariate Analysis of Covariance (one-way MANCOVA) will be conducted. Covariates will reveal if there are any external influencing factors in care or if these are result of within-case (site) effects. Potential covariates will be patient demographics (i.e. age, gender, ethnicity, diagnosis, and civil/family/accommodation/employment status), diagnosis (type of severe mental illness), and service use (informal/formal, frequencies of admissions, length of stay/service use) and clinical variables (number of staff on ward number of patients). If statistically significant differences are found subsequent One-way Analysis of Covariance (One-way ANCOVA) will be employed post hoc to ascertain which measures differ between which locations. Correlations will be carried out to identify if there is a relationship between the outcome measures. The type of correlation that will be performed will be informed by hypotheses

derived from the descriptive data and the qualitative data. Selective correlations will be conducted using Multiple Linear Regression. Similarly a one-way MANCOVA will be conducted to analyse staff questionnaires (RSA and STAR) with appropriate post hoc analyses. A one-way ANCOVA will be used to analyse the carer questionnaire (RSA) and if significant differences are found Tukey's post hoc test will be conducted.

Qualitative analysis

Data from interviews with managers, professionals, carers and service users and from non-participant observations of care planning processes will be transcribed in full. Transcripts, local policy documents and field notes will be anonymised with pseudonyms inserted and person and place identifiers removed. Data will be analysed using the framework method (Ritchie & Spencer 1993) on QSR NVivo10. Our framework will reflect our research questions, allowing us to directly identify instances in our data where local policies, interviewee accounts and observed everyday practice reflect (or do not reflect) commitments to (and experiences of) inpatient mental health care which is coordinated, recovery-focused and tailored to the particular needs and wishes of individuals. We will compare and contrast orientations to recovery and personalisation in local policy and in the accounts of senior managers and professionals with our analysis of actual care as this is provided and received.

Integration of Data

We are employing a concurrent transformative mixed methods design with embedded case studies (Creswell 2009: p15). Concurrent procedures require that we will collect quantitative and qualitative data at the same time during the study and then integrate that data in order to provide a comprehensive analysis of the research problem. One form of data is nested within another larger data collection procedure in order to analyse different questions or levels of units in an organization. In this study, the more detailed qualitative data from indepth interviews, local policy reviews, care plan reviews and observations are nested within larger survey datasets in order to provide potential explanation and understanding of scores on various measures.

Transformative procedures require the researcher to employ a theoretical lens as an overarching perspective within a design that contains both quantitative and qualitative data. This lens provides a framework for topics of interest, methods for collecting data, and outcomes or changes anticipated by the study. In our study, our choice of methods, data collection and approach to analysis is informed by theories of recovery and personalisation. The Framework method will be employed to bring together charted summaries of qualitative data alongside summary statistics of measures of satisfaction with inpatient care and care planning; recovery-orientation of services, quality of therapeutic relationships and empowerment of service users.

We will bring our framework analysis and our analysis of questionnaire data together for each site, noting points of comparison and contrast between what we find in our analysis of each type of data. Where consistently strong orientations to recovery-focused, personalised

care are found in local policy documents and in the accounts of senior managers and practitioners and are reflected in the experiences of users and carers and in our observations of everyday practice we will say so. Where discrepancies are found, or where questionnaire data contrast with data generated through interviews and observations, we will say so.

Armed with our set of six within-case analyses we will then conduct a cross-case analysis to draw out key findings from across all sites (see Figure 2). We will consider the relationships between stated orientations to recovery and personalisation in national and local policy, and in senior staff interviews, and what we have found by studying the accounts of users and carers and by analysing everyday inpatient care. In this way we will consider the relationships between the 'macro, 'meso' and the 'micro', drawing lessons for NHS managers and professionals concerned with the promotion of inpatient mental health care which is aimed at the promotion of recovery and the particular needs of individuals.

